SQIN-01: SQIN-Furosemide and SQIN-Infusor

SQI Inc.

An open label, single dose study to assess safety and efficacy of a novel patch infusor device and novel SUBCUTaneous furosemide formulation combination in patients with Heart Failure: a phase I clinical trial

Protocol

ACRONYM: SUBCUT-HF I

Protocol Version: 1.1
Date: 06/01/2021
EudraCT Number: 2020-005560-57
REC Reference Number: -----
Sponsor's Protocol Number:
Sponsor: SQ Innovation Inc.
Funder: SQ Innovation Inc.
IMP and medical device supplied by SQ Innovation Inc.
Host: NHS Greater Glasgow and Clyde and the University of Glasgow

This study will be performed according to the Research Governance Framework for Health and Community Care (Second edition, 2006) and The Medicines for Human Use (Clinical Trials) Regulations, 2004 SI 2004:1031 (as amended) and World Medical Association Declaration of Helsinki Ethical Principles for Medical Research Involving Human Subjects 1964 (as amended).

Confidentiality Statement

This protocol contains confidential information that must not be disclosed to anyone other than the sponsor, the Investigator Team, host NHS Trusts, regulatory authorities and members of the Research Ethics Committee. The study will be registered on EUDRACT and clinicaltrials.gov.

Study Synopsis:

Title of Study	An open label, single dose study to assess safety and efficacy of a novel patch infusor device and novel SUBCUTaneous furosemide formulation combination in patients with Heart Failure: a phase I clinical trial
Study Centre	1 site in Queen Elizabeth University Hospital in Glasgow
Investigational Product and Medical Device	The drug and device combination is called SQIN-01. SQIN-01 is a combination of SQIN-Infusor and SQIN-Furosemide Investigational pump (SQIN-Infusor, medical device) intended for subcutaneous infusion of investigational product, SQIN-Furosemide. SQIN-Furosemide is investigational subcutaneous furosemide formulation at 30mg/mL at pH 7.4 (range 7.0 to 7.8) intended for slow subcutaneous infusion using a biphasic delivery profile. 80mg of SQIN-Furosemide will be administered using SQIN-Infusor by subcutaneous infusion over 5 hours using biphasic delivery profile of 30mg in the first hour and 50mg over the remaining 4 hours.
Study Phase	I
Primary Objective	To investigate the safety, tolerability, efficacy and on-body performance of a novel patch infusor device and novel furosemide formulation combination (SQIN-01).
Secondary Objective	To investigate the efficacy of SQIN-01 To investigate skin reactions and patient acceptability.
Primary Outcomes	
 • Safety as determined by treatment emergent adverse events (TEAEs), (including serious adverse events [SAEs]) and adverse drug events (ADEs)(including serious adverse drug events [SADEs]) • Infusion site pain measured using a Numerical Pain Rating Scale(1) (Appendix 3) • Any device failures (e.g. adhesive failure and drug delivery failure) • Serum furosemide concentration at 0, 60 and 240 minutes after start of SQIN-Furosemide infusion
Secondary outcomes	
 • Urine volume and sodium concentration in urine collected 8 hours after start of SQIN-Furosemide infusion • Presence of local skin reactions, recorded with photography and assessed using standardised erythema/edema assessment tool (2) (Appendix 4) • Patient acceptability using System Usability Scale(3) (Appendix 5)
Rationale	A new formulation of (neutral pH) furosemide (SQIN-Furosemide) that can be delivered subcutaneously by a pump placed on a patient abdomen has been developed. This trial will test the on-body performance of new subcutaneous pump device (SQIN-Infusor) and clinical efficacy of SQIN-Furosemide in patients with heart failure (HF).

Study design	Prospective, open-label, single dose study in 20 patients previously diagnosed with HF being treated with intravenous furosemide therapy at a dose of ≥ 40 mg/day as in-patients.
Sample Size	20
Screening	Coronary care unit and cardiology wards.
Main Inclusion Criteria	
 • Written informed consent • Male or female ≥ 18 years of age • Meet ESC criteria for diagnosis of HF(4) • Inpatient with a primary diagnosis of HF requiring treatment with intravenous furosemide at dose ≥ 40 mg/day per day
Main Exclusion Criteria	
 • Unable to consent to inclusion in study due to lack of capacity • Requiring treatment with intravenous furosemide at dose > 200 mg per day as determined by the usual care team • Current inotropes, vasopressors or intra-aortic balloon pump therapy • Concomitant use of diuretics in 12 hours preceding administration of study drug with SQIN-Infusor • Systolic blood pressure (SBP) < 90 mmHg • Pregnancy or breastfeeding • Left sided valve disease with planned surgery or percutaneous intervention • Type 1 myocardial infarction during index hospitalisation (type 2 myocardial infarctions are allowed)(5) • Any surgical or medical condition which prevents patient from ambulation during the infusion • Renal impairment, defined as $eGFR < 30$ mL/min/1.73 m² at screening. • Patient on active cardiac transplant waiting list • Potassium < 3.0 mmol/L • Potassium > 6.0 mmol/L • Sodium < 125 mmol/L • Any contraindications for furosemide administration as per furosemide SmPC • Any surgical or medical conditions, which in the opinion of the investigator may pose an undue risk to the subject, interfere with participation in the study or which may affect the integrity of the data
Randomisation	None
Duration of Treatment	5 hours
Statistical Analysis	
Determination of sample size was based on a pragmatic assessment to characterise PK/PD.
 
A statistical plan will include all subjects who were placed SQIN-Infusor and which was activated in accordance with the instructions (Intent to treat). Additional analyses include participants who received 1 dose (80mg) of study drug (SQIN-Furosemide) administered with the investigational pump (SQIN-Infusor).

	
All primary and secondary safety outcomes will be listed by the subject. TEAEs and SAEs will be summarised for each event by system organ class, preferred term, severity, and relationship to study device and drug.
 
Any observed values and changes from baseline for clinical and laboratory data, physical examination results and vital signs will be summarised using appropriate descriptive statistics.
 
Furosemide concentrations at pre-specified times (0, 60 and 240 minutes from start of the infusion) will be summarised using descriptive statistics (including N, mean, standard deviation, coefficient of variation, median, minimum and maximum).
 
Urinary volume and sodium concentration measure at 8 hours will be summarised using descriptive statistics (including N, mean, standard deviation, coefficient of variation, median, minimum and maximum).

--	--

19 APR 2021

1.6.6. SOFTWARE

The statistical software packages used will be R for Windows v3.3.1, SAS for Windows v9.3, or higher versions of these programs.

2. ANALYSIS

2.1. STUDY POPULATIONS

The main analysis population will be all subjects who consented and were placed on the SQIN-Infusor and it was activated in accordance with the instructions.

We will also look at the enrolled population, which is all subjects that have consented into the study and meet the entry criteria.

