2.4. STUDY OUTCOMES

2.4.1. PRIMARY OUTCOMES

The primary outcomes for this study are:

- Safety as determined by treatment emergent adverse events (including serious adverse events) and adverse drug events (including serious adverse drug events)
- Infusion site pain measured using a Numerical Pain Rating Scale

- Any device failures
- Serum furosemide concentration at 0, 60 and 240 minutes after the start of SQIN-Furosemide infusion

The safety primary outcomes (treatment emergent adverse events, and adverse drug events, and device failures) will be listed by subject for all subjects in the main analysis population. Summaries will be presented for the infusion site pain measure and the serum furosemide concentrations at each of the time points.

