2.4.2. SECONDARY OUTCOMES

The secondary outcomes for this study are:

- Urine volume and sodium concentration in urine collected 8 hours after start of SQIN-Furosemide infusion
- Presence of local skin reactions
- Patient acceptability using System Usability Scale

The urine volume, sodium concentration in urine, and the patient acceptability scale will be summarised for the main analysis population

Any local skin reactions will be listed by subject.

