4. TABLE SHELLS

Table 1.1: Study Disposition	
	All
Consented	N
Screen Failures	N (%)
Screen failure reason 1	N (%)
Screen failure reason 2	N (%)
.....	N (%)
Enrolled population (consented and met eligibility criteria)	N
Main analysis population (activated SQIN-Infusor)	N
Completed the study	N (%)
Early termination	N (%)
Reason for early termination	
Adverse Event	N (%)
Subject withdrew consent	N (%)
Withdrawn by investigator	N (%)
Withdrawal by Sponsor	N (%)

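### Device failures are listed only for patients whose pump was placed and activated as instructed, so a failure at activation can drop out of a primary outcome

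*SAP*

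**What the plan says.** The protocol synopsis puts on-body performance of the pump in the primary objective. Among the primary outcomes it names "Any device failures (e.g. adhesive failure and drug delivery failure". The two kinds of failure are given as examples, so the outcome is not confined to them.

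SAP 2.1 defines the main analysis population as the consenting subjects who were "placed on the SQIN-Infusor and it was activated in accordance with the instructions". SAP 2.4.1 then says that the safety primary outcomes, device failures among them, "will be listed by subject for all subjects in the main analysis population". The Statistical Analysis entry of the synopsis uses the same condition for its own main set: subjects fitted with the pump "which was activated in accordance with the instructions (Intent to treat".

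Two other sets appear. The synopsis adds participants who received the single 80 mg dose through the pump. SAP 2.1 adds an enrolled population (consented and eligible), which the investigators will also look at. The SAP text gives that population the summary of non treatment-emergent events (2.9.3) and a count in the disposition table (2.2 and Table 1.1). In Table 1.1 the main set is labelled "Main analysis population (activated SQIN-Infusor".

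**The concern.** A patient enters the set in which device failures are listed only after the device has passed its first test, which is being activated as instructed. A pump that is stuck on but does not start can therefore remove its own patient, and its own failure, from the listing of a primary outcome. An intent-to-treat label on such a set tells the reader the opposite, because membership depends on something that happens after placement.

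Adverse events have a related gap. SAP 2.4.1 lists treatment-emergent and adverse drug events for the same population. Suppose a pump is wrongly activated but still delivers some drug, and an event follows. The patient is outside the main population, and the event is not non treatment-emergent under 2.9.3, because it came after administration. No set clearly captures it.

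At stake is whether this first look at a new pump shows every failure that occurred, or only those that came after a correct start.

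**Working it through.** **Inputs.** The planned sample size is 20 (synopsis). It rests on a pragmatic assessment, with no formula or failure rate, so there is no figure of the plan's own to reproduce. The documents give no number or rate of activation failures; the values of *a* below are assumptions.

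**Step 1: follow one patient through the sets.** Take a patient whose pump is placed but does not activate.

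- Main analysis population: not a member, if activation means that the pump started. No entry in the device failure listing.
- The 80 mg set: not a member, because no dose was delivered.
- Enrolled population: a member, but device failures are not assigned to it.
- Table 1.1: the patient appears only as a difference between the enrolled and main counts. No row covers failed activation, and the early-termination reasons have no device category.

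**Step 2: direction.** Let *P* be patients with the pump placed, *a* those with an activation-stage failure and *f* those with a later failure, with at most one failure per patient.

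- Plan as written: *f* failures among *P* − *a* patients.
- All placements: *f* + *a* failures among *P* patients.
- Difference in count: (*f* + *a*) − *f* = *a*, which is never negative.
- If a reader forms a proportion: (*f* + *a*)(*P* − *a*) − *fP* = *a*(*P* − *a* − *f*), which is also never negative because *f* ≤ *P* − *a*.

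So neither the count nor the proportion can be too high on this account.

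**Step 3: illustrative size, with *P* = 20.** Intervals are exact (Clopper-Pearson) 95%: the lower limit is the 2.5% point of Beta(x, n − x + 1), and the upper limit is the 97.5% point of Beta(x + 1, n − x).

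| *a* | *f* | Plan as written | All placements |
|---|---|---|---|
| 0 | 0 | 0/20 = 0% (0 to 16.8%) | 0/20 = 0% (0 to 16.8%) |
| 1 | 0 | 0/19 = 0% (0 to 17.6%) | 1/20 = 5.0% (0.1 to 24.9%) |
| 2 | 0 | 0/18 = 0% (0 to 18.5%) | 2/20 = 10.0% (1.2 to 31.7%) |
| 2 | 1 | 1/18 = 5.6% (0.1 to 27.3%) | 3/20 = 15.0% (3.2 to 37.9%) |
| 4 | 1 | 1/16 = 6.3% (0.2 to 30.2%) | 5/20 = 25.0% (8.7 to 49.1%) |

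If patients without activation were replaced until 20 were activated, two such cases would give 0/20 against 2/22 = 9.1% (1.1 to 29.2%). The picture is much the same.

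**Step 4: how likely is any loss?** With an assumed activation-failure probability *p* per pump, the chance of at least one case in 20 is 1 − (1 − *p*)^20. This is 18% at *p* = 1%, 33% at 2%, 64% at 5% and 88% at 10%. The expected number lost is 20*p*: 0.2, 0.4, 1 and 2.

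**The case against.** The best reply is that the effect is small and conditional.

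- **No rate is planned.** SAP 2.4.1 promises a listing by subject, with no proportion, interval or test for device failures. This stands: the direct effect is a missing entry in a listing, and the percentages above only show scale.
- **The loss may be nil.** Also true. It occurs only if a pump is placed and not activated as instructed.
- **The named examples mostly survive.** Adhesive or delivery failure after a correct activation stays in the main population. Only placement- and activation-stage failures are at risk.
- **The wording has a milder reading.** Activation according to the instructions may mean only that the user followed the steps. A pump that then failed to start would be kept, while one activated incorrectly would still drop out. The SAP does not settle this. The Table 1.1 label points to the stricter reading, but it is only a label.
- **The shortfall would show.** The disposition table reports the enrolled and main counts, so a gap would be visible. It would not be attributed to the device.
- **The text reviewed is partial.** It comprises the protocol synopsis and the SAP from section 1.6.6 on. A definition of device failure could stand elsewhere.

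A reader might also infer that usability is overstated, since "the patient acceptability scale will be summarised for the main analysis population". That assumes patients without activation would complete the System Usability Scale and score it low. Nothing in the documents shows either. Nor does either document call a use error a device failure, so it cannot be said that use errors are lost from the primary outcome.

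**Conclusion.** The point holds in a limited form. Under SAP 2.1 and 2.4.1 read together, a device failure at activation can fall outside the listing of a primary outcome, and neither of the other sets recovers it. The count of device failures may be too low and cannot be too high. The shortfall equals the number of activation-stage failures; each moves the all-placements proportion by 1/20 = 5 percentage points, and it is zero if every pump activates.

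This rests on the stricter reading of activation and on there being no wider rule for device failures outside the text reviewed. A reader might go further and conclude that the trial's failure rate is biased in favour of the product. The documents do not support that: they give no activation-failure rate and plan no failure rate. What they do contain is a stated rule that can only err in one direction, and it is worth correcting before analysis.

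**What to change.** - In SAP 2.1 and 2.4.1, list and count device failures and device-related adverse events for every patient in whom placement of the pump was attempted, whether or not it activated.
- Record the stage of each failure (placement, activation, delivery), and report incorrect activation separately as a use error.
- Add a row to Table 1.1: *Device placed, not activated as instructed (reason)*.
- Do not call the activated set intent to treat in the protocol synopsis.
- Keep the activated set for serum concentrations and urine outcomes.

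The cost is a few sentences of SAP wording, one change to the synopsis and one table row, with no added patients. The team should confirm that the case report form records placement attempts that did not lead to activation; the text reviewed does not show this. The reported device failure count may come out slightly less favourable.

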2.2. SUBJECT DISPOSITION

The flow of patients in the study will be described according to CONSORT guidelines, with the number and percentage of subjects summarised for the following:

- Consented
- Screen failure (and reasons)
- Withdrawn (and reasons where available)
- Study populations

2.3. BASELINE CHARACTERISTICS

The following baseline characteristics and measures will be summarised for the main analysis population at the first study visit:

- Demographics
- Physical examination
- Vital signs
- Medical history, including HF history and medications
- Blood results, including haematology, biochemistry and biomarkers

2.4. STUDY OUTCOMES

2.4.1. PRIMARY OUTCOMES

The primary outcomes for this study are:

- Safety as determined by treatment emergent adverse events (including serious adverse events) and adverse drug events (including serious adverse drug events)
- Infusion site pain measured using a Numerical Pain Rating Scale

- Any device failures
- Serum furosemide concentration at 0, 60 and 240 minutes after the start of SQIN-Furosemide infusion

The safety primary outcomes (treatment emergent adverse events, and adverse drug events, and device failures) will be listed by subject for all subjects in the main analysis population. Summaries will be presented for the infusion site pain measure and the serum furosemide concentrations at each of the time points.

2.4.2. SECONDARY OUTCOMES

The secondary outcomes for this study are:

- Urine volume and sodium concentration in urine collected 8 hours after start of SQIN-Furosemide infusion
- Presence of local skin reactions
- Patient acceptability using System Usability Scale

The urine volume, sodium concentration in urine, and the patient acceptability scale will be summarised for the main analysis population

Any local skin reactions will be listed by subject.

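### The urine outcome reports volume and sodium concentration separately and, in the visible text, never derives total sodium excreted per patient

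*SAP*

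**What the plan says.** SAP 2.4.2 lists the urine outcome among the secondary outcomes: "Urine volume and sodium concentration in urine collected 8 hours after start of SQIN-Furosemide infusion". Its analysis sentence reads "The urine volume, sodium concentration in urine, and the patient acceptability scale will be summarised for the main analysis population". The Statistical Analysis row of the protocol synopsis says "Urinary volume and sodium concentration measure at 8 hours will be summarised using descriptive statistics" and names the statistics: N, mean, standard deviation, coefficient of variation, median, minimum and maximum.

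Neither document, as shown, defines an amount of sodium excreted or any other per-patient combination of the two values. Nor does either state whether the urine is pooled from infusion start to 8 h or sampled at 8 h.

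The outcome serves the secondary objective "To investigate the efficacy of SQIN-01"; efficacy is also named in the primary objective. The design is "Prospective, open-label, single dose study in 20 patients previously diagnosed with HF", with no randomisation. On sample size the synopsis says only "Determination of sample size was based on a pragmatic assessment to characterise PK/PD".

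**The concern.** A diuretic's effect on sodium is measured by how much sodium leaves the body over a defined period. Concentration is amount divided by volume, so it can be high or low for the same amount removed. A table of concentrations therefore does not describe natriuresis.

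Printing a volume table beside it does not repair this. The two tables summarise the marginal distributions, and the link between one patient's volume and that patient's concentration is gone. A reader of the report cannot rebuild the mean or the standard deviation of sodium excretion.

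This matters because the urine outcome is the only named outcome in the visible text that measures the response to the drug, and the sample size is justified by characterising PK/PD. In a purely descriptive study of 20 patients, the choice of variable to summarise is most of the analysis. As written, the study would report no prespecified measure of sodium removal.

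**Working it through.** **Figure to reproduce.** There is none. The sample size of 20 is called pragmatic and comes with no effect size, SD, alpha or power. The check is therefore whether the planned summaries determine total sodium.

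**Inputs.** From the documents: two variables, volume V and sodium concentration C, summarised separately at 8 h. The documents give no volumes, concentrations, CVs or correlations, so all such values below are assumptions.

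**Step 1: does concentration determine the amount?** Sodium excreted (mmol) = V (L) × C (mmol/L).

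| V (L) | C (mmol/L) | Sodium (mmol) |
|---|---|---|
| 1.0 | 120 | 120 |
| 2.0 | 60 | 120 |
| 3.0 | 40 | 120 |
| 1.5 | 100 | 150 |
| 3.0 | 100 | 300 |
| 3.0 | 90 | 270 |

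A threefold range of concentration (40 to 120) goes with one amount, and one concentration (100) goes with a twofold range of amounts. Comparing the last row with the first, the patient with the lower concentration (90/120 = 0.75) excretes 270/120 = 2.25 times as much sodium.

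**Step 2: can mean excretion be rebuilt from the two means?** E[VC] = E[V]·E[C] + ρ·SD(V)·SD(C), so E[VC] / (E[V]·E[C]) = 1 + ρ·CV(V)·CV(C). The relative error of the product of means is 1 / (1 + ρ·CV(V)·CV(C)) − 1.

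With CVs of 50% and 30%:
- ρ = −0.5: 1 − 0.5 × 0.5 × 0.3 = 0.925; error 1/0.925 − 1 = +8.1%.
- ρ = +0.5: 1 + 0.5 × 0.5 × 0.3 = 1.075; error 1/1.075 − 1 = −7.0%.

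With other assumptions:
- CVs 50% and 30%, ρ = −0.6 to +0.6: +9.9% to −8.3%.
- CVs 40% and 25%, ρ = −0.6 to +0.6: +6.4% to −5.7%.

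The error is zero only when ρ = 0, and the planned summaries do not report ρ.

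**Step 3: can the spread be rebuilt?** It also needs ρ, and the distributional shape as well. With CVs of 50% and 30%, writing a = 0.5 and b = 0.3:
- Bivariate normal: CV² = [a² + b² + 2ρab + a²b²(1 + ρ²)] / (1 + ρab)². At ρ = −0.5, √0.2181 / 0.925 = 50%. At ρ = +0.5, √0.5181 / 1.075 = 67%.
- Lognormal: CV² = (1 + a²)(1 + b²)(1 + ρab)² − 1. At ρ = −0.5, √(1.3625 × 0.8556 − 1) = 41%. At ρ = +0.5, √(1.3625 × 1.1556 − 1) = 76%.

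The loss is larger for the spread than for the mean.

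**Step 4: when is the product valid?** Only when V and C come from the same collection. The synopsis gives an infusion time of 5 hours, so a sample taken at 8 h would fall 8 − 5 = 3 hours after the infusion ends. Its concentration could not be multiplied by the volume accumulated from time 0.

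**The case against.** The strongest reply is that nothing is lost. Volume is summarised in the same sentence as concentration and is a direct measure of diuresis. If both values come from one collection, sodium excretion can be computed for each patient at any time. The error in Step 2 arises only if a reader multiplies the two reported means, which the plan does not propose. All of this stands. It limits the point to an omitted derived variable, but the derivation still needs to be prespecified and reported.

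A reader might go further and infer that the main efficacy readout is confounded by urine volume. The documents do not support that. They present this as one of the items under "The secondary outcomes for this study are", and no outcome is labelled the main efficacy measure. With no comparator and no hypothesis test, there is no effect estimate to confound. Nor do the documents show that concentration falls as volume rises; the argument needs only that concentration depends on volume.

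A reader might also infer that the plan calls for a spot sample at 8 h. That is the weaker reading. One phrase governs both volume and concentration, and a volume implies collection over time. The wording is loose enough to deserve a clarification, no more.

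Finally, only the protocol synopsis is available, one part of the SAP was removed before review, and a single table shell is visible. The collection procedure or the derivation may be stated elsewhere. However, the SAP section that defines the secondary outcomes is visible and does not contain the derivation.

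**Conclusion.** The point holds as an omission in a secondary, descriptive outcome. In the visible text sodium is reported only as a concentration, which is not a measure of natriuresis, and separate summaries recover neither the mean nor the spread of sodium excretion.

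The size is modest for the mean: about −7% to +8% with CVs of 50% and 30% and a correlation of −0.5 to +0.5. It is greater for the spread, where the CV of excretion runs from about 50% to 67% under bivariate normality and 41% to 76% under lognormality on the same inputs. These are illustrations on assumed values, not bounds.

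The diuresis result, the safety outcomes and the serum furosemide outcome are unaffected.

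**What to change.** In SAP 2.4.2:

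1. Add a derived variable for each patient: total sodium excretion over 0-8 h (mmol) = urine volume (L) × urine sodium concentration (mmol/L) of the same collection.
2. Summarise it with the statistics already listed in the protocol synopsis (N, mean, SD, CV, median, minimum, maximum). A 95% confidence interval is optional.
3. Keep volume and concentration as reported now.
4. State that both values come from one pooled collection running from infusion start to 8 h, and align the synopsis wording.

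The cost is one derived variable, one table row and one clarifying phrase. If the urine is already pooled, as the wording most naturally suggests, no procedure and no data collection changes. If it is not, the product would be invalid and the collection itself would have to be settled first.
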